13.0 STATISTICAL CONSIDERATIONS

13.1 Study Design

This study will be conducted as a single center, single agent, phase I/II trial of 8-chloro-adenosine. 8-chloro-adenosine will be administered as a 4 hour infusion daily for 5 days every 4 weeks; treatment cycle length is 28 days.

Phase I:

The primary objective of the phase I study is to determine the recommended phase II dose (RP2D) of 8-chloro-adenosine when given as a single agent, in patients with relapsed or refractory acute myeloid or lymphoblastic leukemia. The dose of 8-chloro-adenosine will depend on dose level assignment.

The phase I study will follow a modified 3+3 design for enrollment with dose escalation, or expansion of a cohort on the basis of the occurrence of dose limiting toxicities (DLTs) during cycle 1. This modified design involves an initial accelerated dose escalation stage (dose-doubling from an initial dose of 100mg/m² to 800mg/m²) that may be ended by a single DLT in cycle 1 or two occurrences of 'moderate' treatment-related toxicity. During the initial accelerated stage of accrual, cohorts of up to 3 patients will be enrolled and the dose level will be escalated by increments of 100% over four doses of 8-chloro-adenosine (dose level 1a: 100mg/m²; dose level 2a: 200 mg/m²; dose level 3a: 400 mg/m² and dose level 4a: 800 mg/m²). If the accelerated dose stage is halted due to toxicity, the study will switch to escalation that includes intermediate doses. The intermediate dose levels -'b' levels, in increments of 50% from the planned four doses, are defined as follows: 150mg/m²; 300 mg/m²; and 600 mg/m². **With Amendment v07:** the starting dose will be 400 mg/m² (dose level 3a).

At the conclusion of the accelerated stage, dose escalation will occur according to the standard 3+3 rules: The highest dose level that produces $\leq 1/6$ DLTs in cycle 1 will be the maximum tolerated dose (MTD). The RP2D of 8-chloro-adenosine will generally be the MTD, but it may be less than the MTD based on a review of available data/cumulative toxicities from phase I. The RP2D identified in the phase I portion of the study will be brought forward for activity evaluation.

Phase I (Evaluable for Toxicity): Patients will be considered evaluable for toxicity if they receive any study drug. To be evaluable in the context of dose escalation, a patient must receive at least 80% of 8-chloro-adenosine and be followed for the full 28 days during cycle 1 or experience a DLT during the first cycle of therapy. All patients who are not evaluable for DLT will be replaced.

Phase II:

The primary objective is to estimate the response rate and to evaluate the antitumor activity of 8-chloro-adenosine, in patients with relapsed or refractory acute myeloid or lymphoblastic leukemia. The primary endpoint is complete remission rate (CR/CRI) and is based on the Döhner, 2010 criteria²⁴. A single cycle of treatment will be given in a 28 day cycle. Each patient's disease status will be evaluated at baseline. Response will be assessed at the end of each cycle/just prior to the start of each cycle.

The phase II portion of this study will implement a Gehan two-stage design to estimate the response rate and to evaluate the activity of 8-chloro-adenosine when given as a single agent [23]. The phase II portion of the study is expected to enroll a minimum of 9 and a maximum of 25 patients. The six patients treated at the RP2D in the phase I portion of the study will count toward the 25 patients required; given this, we expect to enroll only 19 new patients on the phase II trial. The sample size is based on the desire to estimate the response rate with at most 10% standard error, and early stopping if the treatment is unexpectedly ineffective.

At stage 1, 9 patients will be entered on the study. If 0 responses are seen in the first 9 patients treated, the study will be terminated and the true regimen response will be declared $\leq 30\%$. If at least 1 patient responds, the trial will continue to the second stage. Because patients treated during the phase I portion of the trial at the dose selected for the phase II trial will be counted ($n=6$), only 3 additional patients will be enrolled at stage 1. Under this design if the study agent is $>30\%$ effective, there would be 96% chance of at least one success.

At stage 2, 16 additional patients will be entered. This accrual provides for estimation of the response rate with no more than 10% standard error.

Phase II (Evaluable for Toxicity): Patients will be considered evaluable for toxicity if they receive any study drug. Patients enrolled/treated as part of the phase II study will not be replaced based on toxicity.

Phase I and II (Evaluable for Response): For the phase II portion, as part of the primary analysis, patients will be considered evaluable for response if they are eligible, have baseline disease assessments, and receive 2 cycles of protocol treatment or achieve a CR/CRI after 1 cycle of protocol treatment. Patients will have their response classified according to the Dohner 2010 criteria²⁴.

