
Statistical Considerations:
 
Study Design
 
Phase I: The primary objective of the phase I study is to determine the recommended phase II dose (RP2D) of 8-chloro-adenosine when given as a single agent, in patients with relapsed or refractory acute myeloid or lymphoblastic leukemia. The phase I study will follow a modified 3+3 design for enrollment with dose escalation, or expansion of a cohort on the basis of the occurrence of dose limiting toxicities (DLTs) during cycle 1. This modified design involves an initial accelerated dose escalation stage (dose-doubling from an initial dose of 100mg/m² to 800mg/m²) that may be ended by a single DLT in cycle 1 or two occurrences of ‘moderate’ treatment-related toxicity. During the initial accelerated stage of accrual, cohorts of up to 3 patients will be enrolled and the dose level will be escalated by increments of 100%. The accelerated stage will end when two patients encounter moderate toxicity or when one patient encounters DLT during cycle 1. At the conclusion of the accelerated stage, the dose escalation will occur according to the standard 3+3 rules: The highest dose level that produces $\leq 1/6$ DLTs in cycle 1 will be the maximum tolerated dose (MTD). The RP2D of 8-chloro-adenosine will generally be the MTD, but it may be less than the MTD based on a review of available data/cumulative toxicities from phase I. The RP2D identified in the phase I portion of the study will be brought forward for further activity evaluation in the phase II portion.

Phase I/ Evaluable for Toxicity: Patients will be considered evaluable for toxicity if they receive any study drug. To be evaluable in the context of dose escalation, a patient must receive at least 80% of 8-chloro-adenosine and be followed for at least 28 days during cycle 1 or experience a DLT during the first cycle of therapy. All patients who are not evaluable for dose limiting toxicity will be replaced. Patients who are replaced with a moderate toxicity will be used in the decision to stop the accelerated dose-doubling stage.

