6.1.2 Possible anticipated toxicities to 8-chloro-adenosine

Events seen in chronic lymphocytic leukemia patients regardless of attribution that were at least two grades over baseline are listed with the highest grade indicated:

Hematologic: anemia (G3), neutropenia (G4), thrombocytopenia (G3)

Gastrointestinal: abdominal pain (G3), diarrhea (G2),

Metabolic: hypercalcemia (G4), hyperglycemia (G3), hypouricemia (G2),

General/Other: back pain (G3), fever (G2), sunburn (G2), flu syndrome (G2)

Toxicities seen in animal studies (murine and canine) using a range of regimens and doses (Section 2.5) are as follows:

Hematologic: transient thrombocytopenia

Gastrointestinal: vomiting

Renal: elevated BUN, renal nephrosis

General/Other: decreased activity, sloughing of the skin, dyspnea

Toxicities which may be foreseeable based on toxicities seen with other adenosine analogues (Cladribine, Didanosine, Fludarabine, Tenofovir) include the following (note: the asterisk indicates extremely rare but serious events):

Hematologic: thrombocytopenia, neutropenia, anemia, myelosuppression, pancytopenia*

Dermatologic: pruritus, rash, Stevens-Johnson syndrome*, toxic epidermal necrolysis*

Gastrointestinal: vomiting, nausea, diarrhea, abdominal pain, mucositis, stomatitis, anorexia, increased serum amylase, pancreatitis

Hepatic: increased liver enzymes, liver failure*

Metabolic: hyperuricemia

Musculoskeletal: arthralgia, myalgia, bone pain, backache, muscle weakness

Neurologic: headache, peripheral neuropathy, dizziness, insomnia

Renal: increased serum creatinine, renal failure*

Other: anaphylactoid reaction*, alopecia, fatigue, fever, chills, infection, pain, dyspnea, edema, diaphoresis, phlebitis

6.2 Start of Cycle Criteria:

Hematologic toxicities:

- For participants with CR, all hematologic toxicities must resolve to ≤ Grade 2
- For participants without CR, hematologic toxicity maybe of any grade.

Non-hematologic toxicities:

- Non-hematologic toxicities related to study agent must resolve to ≤ Grade 2.
- Non-hematologic toxicities not considered related to study agent may delay of start of cycle criteria per the discretion of the treating investigator.

For holds due to toxicities related to study agent, if the participant does not meet criteria to resume treatment by Day 49 from start of cycle, the participant must permanently discontinue study treatment. See Section 6.3 for dose modifications due to toxicity.

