6.3.2 Dose Modifications and Treatment Interruptions

The table below details the specific dose modifications and treatment interruptions for administration of 8-chloro-adenosine; they are to be used in agreement with the information in Section 6.3.1. Unless listed in Table 6.3.2, treatment will continue without interruption or dose modification. Start of cycle criteria will apply to initiate a new cycle of therapy (Section 6.2).

Table 6.3.2 Dose Modifications and Interruptions to 8-Chloro-adenosine Administration*

Adverse Event	Treatment Modification
Non-Hematologic toxicities considered RELATED to 8-chloro-adenosine in all participants:	
Grade 3 toxicity except for the following: 
 • vomiting, nausea, diarrhea that responds to maximum medical therapy • electrolyte imbalance, fatigue, anorexia, asthenia, stomatitis, mucositis, infection, dermatitis 	Hold study treatment until resolution to \leq Grade 2. Resume at pre-hold dose.
Grade 4 toxicity:	Hold study treatment until resolution to \leq Grade 2. Resume at 1 dose level reduction unless the toxicity is a grade 4 electrolyte imbalance correctable within 48 hours or grade 4 vomiting that responds to maximum medical therapy within 48 hours. In such cases patients can resume treatment at the assigned dose without reduction at the Physician's discretion.
Hematologic toxicity RELATED to 8-chloro Adenosine	
Grade \geq 3 peripheral blood cytopenia not resolving to \leq Grade 2 by day 49 from start of cycle in patients who have less than 5% bone marrow blasts	No additional cycles of study drug will be administered
Other unspecified Non-Hematologic Toxicities considered UNRELATED to study agent	
Other unspecified events of any grade considered unlikely or not related to study agent.	Maintain treatment with study agent. Interruption of study treatment is permitted if the investigator consults with the Principal Investigator to determine that this is in the best interest of the participant.

*: See section 5.2 for additional criteria to resume, make up missed doses.

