12.2 Response

The primary endpoint is complete remission rate (CR + CRi) and is based on the Döhner, 2010 criteria²⁴; calculated as the percent of evaluable patients that have confirmed CR or CRi.

Response criteria will be as follows:

CR: Bone marrow with < 5% blasts by morphology. ANC > 10³/µL, platelets ≥ 10⁵/µL

CRi: Bone marrow with < 5% blasts by morphology, not meeting blood count criteria for CR.

PR: Decrease of at 50% in bone marrow blasts

PD: Bone marrow blasts more than 20% and increase in blasts by over 50%.

HR: improvement in hematologic parameters, but not meeting criteria for PR.

Secondary activity endpoints for this study are as follows:

- Duration of response, defined as the time interval from the date of first documented response (CR+CRi) to documented disease relapse or death whichever occurs first.
- Overall survival, defined as the time interval from date of first dose of study drug to date of death from any cause.
- Event-free survival, defined as the time interval from date of first dose of study drug to first documented disease progression or death from any cause, whichever occurs first.
- Overall response rate (CR/CRI/PR), calculated as the percent of evaluable patients that have confirmed CR or CRi or PR.

12.3 Clinical Pharmacology Endpoints:

- For plasma PK, levels of 8-chloro-adenosine, its deaminated metabolite, 8-chloro-inosine, and its base 8-chloro-adenine will be quantitated in plasma during 5 days of therapy.
- For cellular PK, concentrations of 8-chloro-adenosine and 8-chloro-ATP will be quantitated in circulating leukemia cells in the peripheral blood.
- For urine PK, levels of 8-chloro-adenosine, its deaminated metabolite, 8-chloro-inosine, and its base 8-chloro-adenine will be quantitated in urine during the first 24 hours of therapy.
- For PD, the impact of therapy on endogenous ATP pools, as well as the effect on short-lived mRNA transcripts and proteins will be analyzed in circulating acute leukemia blasts.

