13.2 Definition of Dose-Limiting Toxicity (DLT)/Moderate Toxicity

With Amendment v09: A two level toxicity attribution scale will be used. In terms of attribution, all recorded adverse events will be classified as either related or unrelated to the study drug. Prior to this amendment a five level attribution scale (definite, possible, probable, unlikely, unrelated) was used.

A DLT will be defined as any of the following toxicities that occur during cycle 1, per CTCAE version 4.03, and are considered related to the study drug:

(Note: All adverse events will be considered relevant to determining dose-limiting toxicities and reporting unless the event can clearly be determined to be unrelated to the drug.)

Hematologic toxicities:

- For participants with less than 5% bone marrow blasts by morphology, with the exception of Grade 4 neutropenia, Grade 3 or 4 hematologic toxicity that does not resolve to Grade 2 by Day 49 (21 days after the day 28 cycle).
- For participants with less than 5% bone marrow blasts by morphology, Grade 4 neutropenia (absolute neutrophil count $<0.5 \times 10^9/L$) persisting up to Day 42 after the start of treatment.

Non-Hematologic toxicities:

- Any grade ≥ 3 non-hematologic toxicity for ≥ 7 days, with the exception of nausea not controlled by medical management within 72 hours.
- Any treatment related toxicity that prevents the administration of 80% of 8-chloro-adenosine during the first cycle of therapy.
- Delay in start of cycle 2 by more than 14 days due to drug-related non-hematologic toxicity.

Moderate toxicity will be defined as any grade 2 non-hematologic toxicity and occurs during cycle 1, per CTCAE v4.03, with the exception of:

- Allergic rhinitis
- Fatigue
- Sweating
- Weight gain or loss
- Alopecia
- Dry skin
- Nail or pigmentation changes
- Pruritus
- Hot flashes
- Flatulence
- Mouth dryness
- Nausea and vomiting without the use of maximal anti-emetic treatment
- Sense of smell or taste disturbance
- Erectile impotence
- Irregular menses
- Libido
- Oligospermia
- Tumor lysis syndrome
- Electrolyte/metabolic toxicity unable to be corrected within 48 hours
- Other grade 2 toxicity may be excluded pending PI and Data Safety Monitoring Committee (DSMC) review and approval

(Note: All adverse events will be considered relevant to determining moderate toxicities and reporting unless the event can clearly be determined to be unrelated to the drug.)

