*: Note: Dose de-escalation, escalation or cohort expansion will only take place after 3 patients are fully assessed (assuming the first two patients have yet to experience a DLT) using the Common Terminology Criteria for Adverse Events (CTCAE) of the National Cancer Institute (NCI) version 4.03 following the completion of cycle 1.

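### A patient counts for dose escalation at Day 28, but DLTs for prolonged cytopenia or a delayed cycle 2 cannot be read until about Day 42 or Day 49

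*Combined protocol and SAP*

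**What the plan says.** **When a patient counts.** Section 13.1 requires 80% of the drug and that the patient "be followed for the full 28 days during cycle 1 or experience a DLT during the first cycle of therapy". The synopsis words the same rule as a minimum: "be followed for at least 28 days during cycle 1 or experience a DLT". The escalation rules in Section 13.3 then work on evaluable patients, and 0 DLTs among 3 opens the next dose.

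**When a DLT can be read.** Section 13.2 lists five DLT criteria. Two are hematologic and apply only to patients with under 5% marrow blasts:
- "Grade 3 or 4 hematologic toxicity that does not resolve to Grade 2 by Day 49", with Grade 4 neutropenia carved out;
- Grade 4 neutropenia "persisting up to Day 42 after the start of treatment".

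A third late criterion, a drug-related non-hematologic delay of cycle 2, needs more than 14 days to elapse.

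**When the cohort decision is taken.** The note in Section 13.3 says "Dose de-escalation, escalation or cohort expansion will only take place after 3 patients are fully assessed" and refers to the completion of cycle 1. It names neither Day 42 nor Day 49.

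**Holds on cycle 2.** Section 6.2 requires hematologic recovery for patients in CR, but then states: "For participants without CR, hematologic toxicity maybe of any grade". Table 6.3.2 bars further cycles when a Grade 3 or worse cytopenia has not come down to "Grade 2 by day 49 from start of cycle in patients who have less than 5% bone marrow blasts". Section 10.0 extends a cycle while the next one is on hold.

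**The concern.** The clock that lets a patient count toward escalation stops at Day 28, while the clock for three of the five DLT criteria runs on for two to three weeks. A patient who clears the marrow but stays cytopenic can be entered as free of DLT on Day 28 and meet the DLT definition on Day 42 or 49.

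This matters most in the accelerated stage. From the amended start of 400 mg/m², one DLT should end dose-doubling and expand the current level, with 600 mg/m² as the next step. If that DLT is still unreadable when the cohort is judged, the next cohort can be opened at 800 mg/m².

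Section 13.2 also limits DLTs to events in cycle 1, which leaves unclear whether a Day 42 or Day 49 reading counts at all.

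**Working it through.** **1. Gaps.** The plan's own figure reproduces: 49 − 28 = 21 days, as Section 13.2 states in parentheses. For Grade 4 neutropenia, 42 − 28 = 14 days. For the cycle 2 delay, 28 + 14 = Day 42, so it is readable only after about that day.

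**2. Does the start-of-cycle hold supply the wait?** CR in Section 12.2 needs ANC above 10³/µL, which is 1.0 × 10⁹/L. The Day 42 criterion concerns ANC below 0.5 × 10⁹/L. A patient with under 5% blasts and that count is therefore "not meeting blood count criteria for CR" and is classed as CRi. Section 6.2 lets patients without CR start cycle 2 at any hematologic grade, so this patient may be re-dosed at about Day 29. Table 6.3.2 implies a wait to Day 49 for the same patient. The two rules conflict.

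**3. Are counts scheduled at the read-out?** (Table 10.0 and its footnotes)
- Treatment continues: with cycle 2 Day 1 on Day 29, cycle 2 Days 15 and 22 are Days 43 and 50 (±2). Counts exist but follow new dosing, so they would tend to over-call a cycle 1 DLT rather than miss it.
- Treatment stops after cycle 1: the last scheduled CBC is 30 days after the Day 5 dose, Day 35 ± 2 = Days 33 to 37. That is 5 to 9 days before Day 42 and 12 to 16 days before Day 49.

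**4. How many patients are pending at once?** The synopsis gives 43 patients in 70 months: 70 × 30.44 / 43 = 49.6 days per patient on average. When patient 3 reaches Day 28, patients 2 and 1 are at about Days 78 and 127. The base case therefore has only the last patient unread.

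**5. Effect on the 0-of-3 decision.** Assumptions, none from the documents: marrow clearance in 10% to 30% of patients, and a late cytopenia DLT in 10% to 50% of those. This gives a late rate l of 0.10 × 0.10 = 0.01 to 0.30 × 0.50 = 0.15. The true total DLT rate is taken as 1/3. The first two patients are fully read (clean with probability 2/3 each), and the last looks clean with probability 2/3 + l:

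P(0/3 at Day 28) = (2/3)² × (2/3 + l)

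| l | P(0/3) | excess over full reading, (4/9) × l |
|---|---|---|
| 0 | 0.296 | 0 |
| 0.01 | 0.301 | 0.004 |
| 0.15 | 0.363 | 0.067 |

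The excess is the chance that a cohort clears while holding an unread DLT. The moderate-toxicity stop and the cycle 2 delay criterion are not modeled.

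**6. Chance that someone is dosed in the gap.** With Poisson arrivals at the average rate, a patient arrives within 14 days with probability 1 − exp(−14/49.6) = 0.25, and within 21 days with probability 1 − exp(−21/49.6) = 0.35. Multiplying by the excess gives 0.0044 × 0.246 = 0.001 to 0.067 × 0.345 = 0.023 per cohort. Patients already waiting for a slot would raise this.

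**The case against.** The best defense is that the 28 days only decide who is counted or replaced, that the synopsis makes them a floor, and that the real trigger is the full assessment in Section 13.3. On an ordinary reading, a patient with an open Day 42 or Day 49 criterion is not fully assessed. A careful team may well wait. But the term is undefined and anchored to the end of cycle 1, and the escalation rule counts patients whom Section 13.1 already calls evaluable. The text permits either course.

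A reader might infer that no hold ever supplies the wait. The documents do not support that. CR has no hemoglobin requirement, so a CR patient can have Grade 3 or 4 anemia. Section 6.2 then holds cycle 2, and Section 10.0 extends cycle 1, so cycle 1 is not complete. The same extension helps when cycle 2 is held for related non-hematologic toxicity, if the team takes Section 13.3 to mean the extended cycle. What is left open is chiefly CRi.

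For CRi, Table 6.3.2 makes sense only if cycle 2 waits, and Section 6.3.1 sets the same Day 49 limit on holds. That is a fair argument about intent, but Section 6.2 says the opposite.

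The branch in which treatment stops after cycle 1 is narrow. Non-progressing patients have response assessments in active follow-up that need counts to separate CR from CRi, and Section 10.0 allows extra procedures when clinically indicated. Still, no CBC is scheduled there.

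A reader might also apply the whole 3+3 escalation probability (43% to 50%, against 43%) to the jump to 800 mg/m². That figure includes the route through 1 DLT in 6. A DLT ends acceleration, so that route leads from 400 to 600 mg/m². Only the 0-of-3 figure bears on doubling.

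**Conclusion.** The point stands on the text: a stated rule lets the next dose open 14 to 21 days before a DLT that the plan itself defines can be read, and no sentence orders a wait. It should be fixed, although its practical size is probably small, because few patients with relapsed or refractory AML are likely to reach under 5% blasts.

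On the assumed range, a cohort looks clean with probability 30% to 36%, against 30%; at the low end the change is under half a percentage point. The upper end takes marrow clearance at 30%, the rate the plan calls promising, and half of those patients with a late DLT. Simultaneous entry of all three patients would give 31% to 55% ((2/3 + l)³), but that departs from the plan's average accrual.

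A reader might infer that the RP2D will be wrong. The documents do not show this: a late DLT can still enter the count of at most 1 in 6 that defines the MTD, and the review that sets the RP2D. The harm supported is possible early exposure of the next cohort.

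**What to change.** - **Sections 13.1 and 13.3:** state that a patient is not fully assessed if, at Day 28, there are under 5% blasts with an unresolved Grade 3 or 4 cytopenia, or if cycle 2 is being held for drug-related non-hematologic toxicity. Allow no escalation and no MTD declaration until resolution or the applicable read-out: Day 42, Day 49, or more than 14 days of cycle 2 delay.
- **Section 13.2:** state that the cycle 1 limit refers to onset.
- **Table 10.0:** add CBCs at Days 42 and 49 for these patients, including those who stop treatment.
- **Section 6.2 and Table 6.3.2:** reconcile them for CRi. Whether CRi patients should be held is a treatment choice for the investigators; the escalation fix does not depend on it.

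The cost is a few sentences, one or two CBCs per affected patient, and a wait of up to two to three weeks in affected cohorts only. Marrow status is normally known by Day 28, since the biopsy falls on Days 22 to 28, and the wait fits the existing Day 49 limit on holds. All other patients still clear at Day 28.

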5.5 Agent Administration

8-Chloro-adenosine will be administered as an intravenous infusion daily for the first 5 days of each cycle, based on the BSA calculated from the weight measurement taken on Day 1 of the treatment cycle. See Section 8.1.4 for agent preparation. 8-chloro-adenosine will be infused over 4 hours +/- 10 minutes. The infusion rate should not exceed 500 ml/hr. Infusion line will be flushed with 5% dextrose after completion of infusion. Infusion is to be completed within 12 hours of agent preparation during which time it should be stored at room temperature.

Start of cycle criteria are listed in Section 6.2.

Dose levels for dose modification are detailed in Table 5.3.1. There will be no intra-patient dose escalation; participants will undergo dose modification due to toxicity per Section 6.3.2.

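### A related severe non-hematologic event that is cut short when an adequately dosed phase I patient leaves before Day 28 can drop out of the escalation count through the replacement rule

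*Combined protocol and SAP*

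**What the plan says.** **Evaluability and replacement.** Section 13.1, under Phase I (Evaluable for Toxicity), asks for at least 80% of the drug and that the patient "be followed for the full 28 days during cycle 1 or experience a DLT during the first cycle of therapy". The next sentence reads: "All patients who are not evaluable for DLT will be replaced". It sets no condition on why the patient became non-evaluable. The synopsis has the same rule in substance and adds a sentence that Section 13.1 lacks: "Patients who are replaced with a moderate toxicity will be used in the decision to stop the accelerated dose-doubling stage".

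**DLT definition.** Section 13.2 gives three non-hematologic routes, each for related events in cycle 1:

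1. Grade 3 or higher for at least "7 days, with the exception of nausea not controlled by medical management within 72 hours".
2. "Any treatment related toxicity that prevents the administration of 80% of 8-chloro-adenosine during the first cycle of therapy".
3. Cycle 2 starting more than 14 days late because of drug-related non-hematologic toxicity.

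The hematologic routes run to Day 42 or Day 49 and apply only with under 5% marrow blasts. None of these clauses addresses death, Grade 5, or an event unresolved when follow-up ends.

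**Moderate toxicity.** Section 13.2 also states: "Moderate toxicity will be defined as any grade 2 non-hematologic toxicity and occurs during cycle 1", followed by a list of exceptions.

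**Dosing.** Section 5.5 specifies an "intravenous infusion daily for the first 5 days of each cycle".

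**Use of the count.** In Section 13.3, 0/3 leads to the next dose, 1/3 adds three patients, 1/6 allows escalation to continue, and 2/3 or at least 2/6 stops it. In the accelerated stage a single DLT ends dose-doubling.

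**The concern.** Replacement is harmless when the reason for leaving has nothing to do with the drug. It is informative when a patient leaves while a related severe event is still running. That patient's DLT status is censored rather than negative, yet the rule removes the patient and fills the place with someone who either completed 28 days or had a declared DLT. The observed DLT proportion is then too low, and the error runs toward escalation and a higher MTD.

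The synopsis sentence on replaced patients shows that the authors saw part of the problem. Read literally, however, it rescues a Grade 2 event and not a truncated Grade 3 or 4 event.

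**Working it through.** **The plan's own figures.** The documents state no operating characteristic for the replacement rule. The nearest figures are the totals, and they reproduce: 6 × 4 = 24 in phase I at most, 25 − 6 = 19 new phase II patients, 24 + 19 = 43. These sums contain no allowance for replaced patients.

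**Step 1: who falls in the gap.** 0.80 × 5 infusions = 4 infusions, so the gap opens with the fourth dose (Day 4 at the earliest) and closes when 28 days of follow-up are complete. Example: all 5 doses given, related Grade 4 non-hematologic event on Day 10, consent withdrawn on Day 14.

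- Route 1: 14 − 10 = 4 days, which is less than 7. Not met.
- Route 2: 5/5 doses given. Not met (with 4/5 = 80% it would also not be met).
- Route 3: a patient who has left has no delayed cycle 2. Not met.
- Follow-up: under 28 days, so not evaluable and replaced.

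**Step 2: effect of one such patient.** If the event would have been a DLT, counting it among the first three gives 1/3 (three more patients) where replacement followed by no further DLT gives 0/3 (next dose). With one other DLT at the dose, it gives 2/6 (stop) where replacement gives 1/6 (continue).

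**Step 3: how often (assumption only).** Let q be the chance that a patient has such a truncated event. P(at least one among n) = 1 − (1 − q)^n.

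| Assumed q | n = 3 | n = 6 |
|---|---|---|
| 1% | 3% | 6% |
| 2% | 6% | 11% |
| 10% | 27% | 47% |
| 20% | 49% | 74% |

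**Step 4: effect on the 3+3 decision (assumption only).** Let p be the true rate of events that would be DLTs if fully observed, and f the share of them lost through replacement. Because a lost patient is redrawn, the rate among counted patients is p′ = p(1 − f)/(1 − pf). The chance of escalating is (1 − p′)³ + 3p′(1 − p′)² × (1 − p′)³.

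For p = 0.33 and f = 0.25: p′ = 0.2475/0.9175 = 0.270, and the chance is 0.557.

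| Assumed p | f = 0 | f = 10% | f = 25% | f = 50% |
|---|---|---|---|---|
| 0.20 | 0.709 | 0.744 | 0.798 | 0.887 |
| 0.33 | 0.434 | 0.480 | 0.557 | 0.714 |
| 0.40 | 0.309 | 0.351 | 0.428 | 0.600 |
| 0.50 | 0.172 | 0.203 | 0.265 | 0.428 |

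The two tables connect through p × f, the per-patient chance of losing a would-be DLT: 0.20 × 0.10 = 2%, and 0.33 × 0.25 = 8%. q is at least this large, since it also includes events that would have resolved before 7 days.

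**The case against.** Several protections narrow the point, and most of them stand.

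- **The reason for leaving is not wholly ignored.** Route 2 counts any related toxicity that prevents 80% of the drug, whatever its duration. Section 6.3.2 holds treatment for most related Grade 3 and all related Grade 4 non-hematologic events, and Section 5.2 limits make-up doses. Severe toxicity before the fourth dose is therefore largely captured.
- **Death.** A related death is Grade 5 and never resolves, so it can be read as meeting the 7-day criterion. The note in Section 13.2, which treats every event as relevant unless clearly unrelated, supports that reading. The text does not settle it, so this is ambiguity and not a certain loss.
- **Stopping treatment is not leaving follow-up.** Section 5.7 speaks of withdrawing from the treatment phase, and Section 5.8 and footnotes g and o of Table 10.0 continue follow-up of serious events. Their duration would normally be observed. Section 5.10 blurs this by listing unacceptable toxicity and refusal of further therapy as ends of participation, but the clear gap is consent withdrawal or loss to follow-up.
- **The toxicity does not vanish.** Anyone given any drug stays evaluable for toxicity (13.1), the PMT log and report cover dose decisions (7.2), the DSMC reviews toxicities quarterly (13.6), and the RP2D may be set below the MTD (13.4). These allow judgment after the fact; they do not alter the count that Section 13.3 acts on.
- **Section 13.3 is not uniformly restricted to evaluable patients.** Only the 0/3, 1/3 and 1/6 rules use that word. This does not help the patient in the gap, whose event is not a DLT under any rule.
- **The frequency is unknown.** q requires a related severe event, adequate dosing, early departure and a short duration together. Entry requires a life expectancy above 3 months. Nothing in the documents supports 10% or 20% over 1% or 2%.

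**Conclusion.** The point holds in a narrow form. Followed literally, the synopsis and Sections 13.1 and 13.2 replace a patient who received at least 80% of cycle 1 drug and then left before Day 28 with an unresolved related Grade 3 or higher non-hematologic event under 7 days old. The gap is clear for consent withdrawal and loss to follow-up, and ambiguous for death. The event leaves the escalation count only. One such patient can change a dose decision, and the direction is toward escalation.

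The size rests on assumed rates: 3% to 49% for at least one such patient among 3 as q runs from 1% to 20%. The documents do not place the trial within that range.

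A reader might infer that the rule disregards toxicity whenever a patient leaves early, that related deaths are certainly discarded, or that the DLT rate is biased by a known amount. The documents support none of these: toxicity that blocks dosing is a DLT, the death case is unstated, and no departure rate is given. Nor would every truncated event have become a DLT. Repeated doublings are also not at issue now: since amendment v07 the start is 400 mg/m², which leaves one doubling, to 800 mg/m².

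**What to change.** Reconcile the synopsis and Sections 13.1 and 13.2 on three matters.

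1. **Classify before replacing.** If a patient would be replaced and there is a death, or a Grade 3 or higher event unresolved at last follow-up, and it is not clearly unrelated to study drug (the attribution standard already in Section 13.2), the PMT/DSMC adjudicates DLT status before the next dose decision. The event is not taken by default to have lasted under 7 days. If judged a DLT, the patient is evaluable and counted; otherwise the patient may be replaced as now.
2. **Do not keep incompletely observed patients as non-DLTs.** Retaining everyone whose departure is not clearly unrelated would add unproven non-events to the denominator and make 0/3 easier to reach, which is the same bias by another path.
3. **Align the carry-over sentence.** State in both the synopsis and Section 13.1 that moderate or worse toxicity in a replaced patient counts toward ending dose-doubling. The Grade 2 wording also leaves out a short Grade 3 event in a fully followed patient, so the text should treat both kinds of patient alike.

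The cost is protocol wording and an occasional adjudication. The downside is that a cohort may be expanded that would otherwise have escalated.
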